2.2.1 Subgroup of interest

Not applicable

2.3 Patient disposition, demographics and other baseline characteristics

Demographic and baseline characteristics of all patients in the extension study will be summarized for the safety population.

2.3.1 Patient disposition

A summary table will be presented including the number and percentage of participants

- Who completed the study
- Who discontinued from study (overall and by the primary reason for discontinuation)

A listing of all participants excluded from any analysis sets will be provided with reasons for exclusion (i.e., including both protocol and non-protocol deviations).

2.3.2 Demographics and other baseline characteristics

Demographics and other extension study baseline data that will be assessed will be summarized descriptively utilizing the safety set. Categorical data will be presented as frequencies and percentages. For continuous data, mean, standard deviation, median, minimum, and maximum will be presented. For selected parameters, 25th and 75th percentiles will also be presented.

Participant demographics will include age, gender, race, ethnicity & BMI.

Relevant medical history and current medical conditions at the baseline will be listed by participant.

2.4 Treatments (study treatment, rescue medication, concomitant therapies, compliance)

The Safety set will be used for treatment related summaries. Categorical data will be summarized as frequencies and percentages. For continuous data, N, mean, standard deviation, median, 25th and 75th percentiles, minimum, and maximum will be presented.

2.4.1 Study treatment / compliance

The study medication (LTP001 [] mg) will be taken daily over 52 weeks at approximately the same time each day [] . []

Compliance will be assessed by the investigator and/or study personnel at each visit using pill counts (if applicable) and information provided by the participant. This information will be captured in the source document at each visit. All study treatment dispensed and returned will be recorded in the Drug Accountability Log.

Remote treatment administration compliance will be assessed by the off-site healthcare professional and information provided to the Investigator and/or study personnel.

Pill counts (including counts of dispensed/returned pills) will be listed by participants, and visits, with relevant information about compliance provided by the participant if data is available.

The duration of exposure (in weeks) will be summarized by means of descriptive statistics using the safety set.

2.4.2 Prior, concomitant and post therapies

Concomitant medications and significant non-drug therapies prior to and after the start of the study treatment will be listed according to the Anatomical Therapeutic Chemical (ATC) classification system.

2.5 Analysis supporting primary objective(s)

The primary aim of the study is to assess the long-term safety of LTP001 in participants with PAH.

2.5.1 Primary endpoint(s)

Safety assessment will include AEs, SAEs, vital signs, ECGs, and safety laboratory measurements.

Adverse events (AEs)

All Adverse events in the extension study will be summarized and listed. Also, all study emergent AEs in both the parent study and extension study will be summarized.

Consistent with the parent study CLTP001A12201 definitions, AEs starting after the first dose of study medication or events present prior to start of treatment but increased in severity based on preferred term will be classified as a treatment emergent AE. The definition of the on treatment period is defined in [Section 2.1.1](#). The following treatment emergent adverse events summaries will be produced:

- by primary system organ class and preferred term
- by primary system organ class, preferred term and maximum severity
- by Standardized MedDRA Query (SMQ) and preferred term.

The number and percentage of participants with adverse events will be summarized.

Separate summaries will be provided for study medication related adverse events, serious adverse events, other significant adverse events leading to discontinuation. In case of sparse events in any of these categories occur, only a listing will be provided if deemed adequate.

The number and percentage of deaths, including on-treatment and post-treatment deaths, will be summarized and listed.

Adverse events of special interest/grouping of AEs is not defined in this study.

Vital signs

Vital signs will include the collection of otic or oral body temperature (recorded in °C), blood pressure (BP) and pulse measurements.

All vital signs data will be listed by participant, and visit/time and if ranges are available, abnormalities will be flagged. Summary statistics (including N, mean, SD, minimum, median, maximum) of vital signs and changes from baseline will be provided by visit/time. Graphical presentations (e.g., boxplots) of vital signs will be provided by visit/time.

Electrocardiogram (ECG)

All ECG data, including PR, QRS, QT, QTcF and RR, will be listed by participant and visit/time, and abnormalities will be flagged. Summary statistics and graphical presentations (e.g. boxplots) will be provided by visit/time.

Categorical Analysis of QTcF (Fridericia's formula) interval data based on the number of participants meeting or exceeding predefined limits in terms of absolute QT or QTc intervals or changes from baseline will be presented. The number and percentage of participants with clinical notable QTcF will be summarized by visit. A listing of these participants will be provided. The clinical notable criteria for QTcF (Fridericia's formula) are indicated in [Table 2-2](#).

Table 2-2 Clinical notable criteria for QTcF (Fridericia's formula)

ECG parameter (unit)	Clinically notable range
Notable value considering newly occurring or worsening cases	
QTcF (msec)	> 500
QTcF (msec)	> 480 if normal at baseline
QTcF (msec)	> 450
Notable change from baseline	
QTcF (msec)	> 60
QTcF (msec)	> 30

Laboratory data

All laboratory data will be listed by participant and visit/time and if normal ranges are available, abnormalities will be flagged. A separate listing is provided presenting all parameters in a subject with any abnormal values. Descriptive statistics (N, mean, SD, minimum, median, and maximum) summarizing continuous laboratory results of clinical chemistry, hematology, urinalysis, and changes from baseline by visit/time will be provided. Graphical presentations (e.g., boxplots) will be provided by visit/time.

Shift tables using the low/normal/high/ (low and high) classification will be used to compare baseline to the worst on-treatment value.

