2.1.1 General definitions

Investigational treatment will be LTP001.

Date of first administration of study treatment (Day 1) will be defined as the date of the first actual administration of LTP001.

Date of last administration of study treatment will be defined as the date of the last actual administration of LTP001.

Two *Baselines* will be defined as the following:

Baseline of the Parent study: the Day 1 assessment of study LTP001A12201. If this datum is not available, the last pre-dosing assessment will be considered.

Baseline of the Extension study: Week 25 visit from LTP001A12201. If this datum is not available, the last pre-dosing assessment for this study (LTP001A12201E1) will be considered. *Study day* will be defined as the number of days since the date of first dose of study treatment (LTP001 or placebo). The date of first dose of study treatment will be defined as *Day 1* and the day prior to first dose of will be defined as *Day -1*. Therefore, for a particular date, study day will be calculated as follows:

for dates on or after the date of first dose of study treatment,

Study day = Assessment date – Date of first dose administration + 1

The on-treatment period lasts from the date of first administration of study treatment to the End of Study (EOS) visit or the date of last randomized dose if EOS visit is not available. The EOS visit is a follow-up visit that is approximately 30 days after the date of the last actual administration of investigational treatment. For participants who will be enrolled into the open label extension (OLE) study, their EOS visits will be skipped.

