2.2 Analysis sets

For all analysis sets, participants will be analyzed according to the study treatment(s) received. The safety analysis set will include all participants that received any study treatment.

The PD analysis set will include all participants who received study treatment and had no protocol deviations with relevant impact on PD data.

The analysis sets and protocol deviation codes are related as [Table 2-1](#).

Table 2-1 Protocol deviation codes and analysis sets

Category Deviation code	Text description of deviation	Data exclusion
Subjects are excluded from Safety analysis in case of these PDs:		Exclude subject from Safety analysis set
INCL01	Subject withdrew consent but continue to receive study medication	Y
Subjects are excluded from PD analysis in case of these PDs:		Exclude subject from PD analysis sets
INCL01	Subject withdrew consent but continued to receive study medication	Y

Protocol deviations mentioned above, and analysis sets will be reviewed in the data review meeting to decide inclusion or exclusion of participant(s) from analyses sets. Decisions regarding the exclusion of participants and/or participant data from analyses will be made prior to final database lock (DBL).

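### The combined parent and extension AE summary is not split by treatment at onset, and SAP 2.1.1 gives two first-dose anchors, so placebo-period events can be counted with LTP001 events

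*SAP*

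**What the plan says.** SAP 2.5.1 plans two AE outputs. The first covers the extension alone: "All Adverse events in the extension study will be summarized and listed". The second is additional: "all study emergent AEs in both the parent study and extension study will be summarized". Protocol 9.3.1 plans the same two outputs. Neither document defines study emergent.

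Treatment-emergent AEs are "AEs starting after the first dose of study medication or events present prior to start of treatment but increased in severity based on preferred term". They are tabulated by system organ class and preferred term, by maximum severity and by SMQ, as numbers and percentages of participants. SAP 2.5.2 limits the primary analysis to counts and summary statistics. Exposure in weeks is summarized separately (SAP 2.4.1).

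SAP 2.1.1 fixes the first dose in two ways. One is LTP001 only: "Date of first administration of study treatment (Day 1) will be defined as the date of the first actual administration of LTP001". The other, used for study day, is "the number of days since the date of first dose of study treatment (LTP001 or placebo". The on-treatment period is not divided at the switch: "The on-treatment period lasts from the date of first administration of study treatment to the End of Study (EOS) visit".

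The general rule in SAP 2.2 is: "For all analysis sets, participants will be analyzed according to the study treatment(s) received". The efficacy endpoints in SAP 2.6.1.1 are explicitly split by parent treatment group and overall. The AE text has no matching instruction.

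**The concern.** Participants who took placebo in the parent study enter the extension (Protocol 1.1 and 2.3). A summary of both studies therefore includes their placebo weeks. If emergence runs from the first dose of any study medication, an AE that began and ended on placebo is a valid entry in that summary. Nothing in the AE text then separates it from an LTP001 event.

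Exposure is a second difficulty. In the combined summary, participants from the parent LTP001 arm contribute both studies on LTP001, while switchers contribute only the extension. A crude percentage grows with time observed, so one figure over both groups does not correspond to a defined length of LTP001 treatment.

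This matters because long-term safety is the primary objective, and the combined summary is the only planned AE output that covers the whole LTP001 exposure of the parent LTP001 arm.

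**Working it through.** The documents state no AE rate and no sample size calculation, so there is no figure to reproduce. The check compares the definitions and then sizes the effect under stated assumptions.

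**1. The definitions applied to one switcher.** Take an AE that starts and resolves at mid-point of the parent study, on placebo.
- Anchor at first LTP001 dose: onset precedes Day 1, so the AE is not treatment emergent.
- Anchor at first dose of LTP001 or placebo: onset follows Day 1, so the AE is treatment emergent.
- SAP 2.5.1 says only "AEs starting after the first dose of study medication", which does not choose between them.

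For a switcher the two anchors lie about 24 weeks apart.

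**2. Inputs.**
- N = about 40 (Protocol section 5).
- Parent treatment ends at Week 25 (SAP 1.1). In Protocol Table 1-2, Week 5 is Day 29. If the parent study uses the same convention, Week 25 is Day 169, which is 24 weeks after Day 1.
- The last extension treatment visit is Day 358, which is 51 weeks after Day 1. Nominal figures are 25 and 52 weeks.
- Assumed: share f of participants from placebo is 1/3 to 1/2; AE rates are constant; follow-up is complete.

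**3. Placebo share of combined person-time.** Total = 40 × (24 + 51) = 3000 weeks.
- f = 1/3: 13.33 × 24 = 320 weeks, and 320/3000 = 10.7%.
- f = 1/2: 20 × 24 = 480 weeks, and 480/3000 = 16.0%.
- With nominal 25 + 52 weeks, the total is 3080 and the shares are 333/3080 = 10.8% and 500/3080 = 16.2%.

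**4. LTP001 exposure by parent arm.** 75 weeks against 51, a ratio of 75/51 = 1.47. Nominally 77 against 52, a ratio of 1.48.

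**5. Crude percentage with at least one AE.** Let E = 51/52.18 = 0.977 years and P = 24/52.18 = 0.460 years, with yearly rates λL on LTP001 and λP on placebo.
- Parent LTP001 arm: 1 − exp(−λL(E + P))
- Switchers, all onsets: 1 − exp(−λL·E − λP·P)
- Switchers, LTP001-period onsets only: 1 − exp(−λL·E)
- Whole table: weights (1 − f) and f.

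For both rates at 0.5: over 75 weeks, 1 − exp(−0.719) = 51.3%; over 51 weeks, 1 − exp(−0.489) = 38.7%. The combined figure is 51.3%. Counting only LTP001-period onsets gives (2/3)(51.3) + (1/3)(38.7) = 47.1% for f = 1/3, and (51.3 + 38.7)/2 = 45.0% for f = 1/2.

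| λL | λP | Combined, f = 1/3; 1/2 | LTP001 onsets only, f = 1/3; 1/2 | Excess (points) |
|---|---|---|---|---|
| 0.5 | 0.5 | 51.3%; 51.3% | 47.1%; 45.0% | 4.2; 6.3 |
| 0.5 | 0.2 | 48.9%; 47.7% | 47.1%; 45.0% | 1.8; 2.7 |
| 0.2 | 0.5 | 28.2%; 29.8% | 22.6%; 21.4% | 5.6; 8.4 |
| 0 | 0.3 | 4.3%; 6.4% | 0%; 0% | 4.3; 6.4 |
| 0.3 | 0 | 31.8%; 30.2% | 31.8%; 30.2% | 0; 0 |

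**6. Direction.** With the same participants in the denominator, adding placebo-period onsets can only turn a participant without an AE into one with an AE. The percentage rises or stays the same. A person-time rate on unsplit data behaves differently. With λL = 0.5 and λP = 0.2 it would be 0.893 × 50 + 0.107 × 20 = 46.8 per 100 person-years (f = 1/3), or 0.84 × 50 + 0.16 × 20 = 45.2 (f = 1/2), against 50 on LTP001. Adding a rate without the split would therefore create a pull towards placebo that the crude percentage does not have.

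**The case against.** The strongest reply is that the main AE output is sound. The extension-only summary comes first in both documents, everyone in it takes LTP001, and SAP 2.5.2 places the evaluation of long-term safety in the extension study. The combined summary is an addition. This stands. A reader might infer that the primary safety result as a whole mixes placebo and LTP001 events; the documents do not support that.

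A reader might also infer that the plan clearly decides to pool. It does not. On the LTP001 anchor, placebo-period AEs are not treatment emergent. The definition also follows the parent study's, which is not available here, and table layouts may sit in other reporting documents. That is fair, but two anchors giving different tables are a defect in themselves, and the SAP is where the choice belongs. The treatment-received rule in SAP 2.2 does not settle it: every treated extension participant received LTP001, and the rule does not say where a switcher's placebo-period event goes.

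A third tempting reading is that placebo events bias the AE result towards placebo and could hide an LTP001 signal. For the planned metric this is wrong, as step 6 shows.

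Finally, exposure is summarized, planned extension exposure is the same in both parent groups, and person-time rates add limited precision with about 40 participants. All true for the extension-only table. In the combined table, a separate exposure summary does not tell the reader what length of LTP001 treatment a percentage refers to.

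**Conclusion.** The point holds for the additional combined summary only. Treatment at onset is not specified there, the first-dose anchors in SAP 2.1.1 conflict, and the only metric is a crude percentage over LTP001 exposures that differ about 1.5-fold. Following the text can place placebo-period AEs in an LTP001 safety table.

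The size is moderate and rests on assumed allocation and rates. About 11-16% of combined person-time is placebo, and the crude percentage exceeds the LTP001-period figure by 0 to about 8 points in the scenarios shown. At equal rates of 0.5 per year it is about 51% against 45-47%. The error is towards attributing too much to LTP001. The clearest case is an event seen only on placebo, which could appear in 4-6% of participants in the combined table with none on LTP001.

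The denominator is also unstated. If parent participants who did not enter the extension were included, these figures would change.

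**What to change.** In SAP 2.1.1, set one anchor for LTP001 safety, the first LTP001 dose in either study, and label any study day counted from parent randomized treatment separately. In SAP 2.5.1:
- Define treatment-emergent for LTP001 as onset, or worsening by preferred term, after the first LTP001 dose, and either define study emergent or drop the term.
- In the combined summary, classify each AE by the treatment being taken at onset. Show the parent placebo period in its own column, and the LTP001 period by parent arm and in total. Keep placebo-period AEs out of the LTP001 total.
- Beside the percentages, give rates per 100 person-years, with person-time restricted to the same treatment period as the events.
- State who is in the combined denominator.

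Apply the same anchor to the other outputs that use the on-treatment period or treatment start date: deaths, worst on-treatment laboratory shifts and AE date imputation.

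The cost is SAP wording and one extra table layout. Parent treatment codes are needed at final analysis, but the efficacy tables already need them. The rates are descriptive, so the statement that no models are used still holds.

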2.5.2 Statistical hypothesis, model, and method of analysis

The long-term safety of LTP001 will be evaluated in this extension study.

All analyses will be based on frequency counts and summary statistics. No statistical models will be used.

The primary analysis population will be the Safety analysis set.

2.5.3 Handling of intercurrent events

Not applicable.

2.5.4 Handling of missing values not related to intercurrent event

Detailed imputation rules are listed in [Section 5.1](#). No additional imputation will be applied to the missing data.

2.5.5 Sensitivity analyses

Not applicable.

2.5.6 Supplementary analyses

Not applicable.

2.6 Analysis supporting secondary objectives

2.6.1 Secondary endpoint(s)

The secondary objectives of the study include assessing the effect of LTP001 on 6MWD, hemodynamic parameters derived from Right Heart Catheterization (RHC), the measurements of right ventricular function (RVF), time to clinical worsening (TTCW), and N-terminal fragment of the prohormone B-type natriuretic peptide (NT-proBNP).

2.6.1.1 Efficacy and/or pharmacodynamic endpoints(s)

All analyses will be conducted using PD analysis set.

Change from baseline for efficacy endpoints will be descriptively summarized by visit/time for treatment group assigned in the parent study, and overall. Two baseline measurements will be generated as per [Section 2.1.1](#). Graphs (e.g., spaghetti plot) will be provided to show individual time courses of parameters for the extension study together with the parent study.

Additionally, two changes from baseline values for efficacy endpoints will be descriptively summarized by visit/time for treatment group assigned in the parent study, and overall with the following comparisons:

- a) Short-term (change from baseline of extension study) vs. long-term (change from baseline of the parent study) treatment effect (For both treatment and placebo groups assigned in the parent study).
- b) the treatment group difference (assigned in the parent study) within each change from baseline value.

6MWD

This measures how many meters a person can walk in 6 minutes. It includes total distance walked (6MWD), the number and duration of any stops in 6 minutes. Test performed at baseline and at visits on Day 176 and 358 will be used for analysis.

Descriptive statistics (N, mean, SD, CV% mean, geometric mean, CV% geometric mean, median, min, and max) summarizing 6MWD parameters and their changes from baseline will be summarized by visit/time for treatment group assigned in the parent study and overall.

Panels of individual spaghetti plots over time/visit for treatment group assigned in the parent study and overall for each 6MWD parameter will be provided.

All 6MWD parameters will be listed by participant, and visit and if ranges are available, abnormalities will be flagged.

RHC

The RHC is performed to assess several hemodynamic parameters when the patient is in a stable hemodynamic rest state (as demonstrated by three consecutive cardiac output measurements with 10% of each other). The measurement is taken at baseline and at visit on Day 176. The assessed hemodynamic parameters include:

- PVR
- right atrial (RA) pressure
- mean pulmonary artery pressure (mPAP)
- pulmonary capillary wedge pressure (PCWP)
- systolic and diastolic blood pressure (RV pressures)
- heart rate (HR)
- cardiac output (CO)
- systemic vascular resistance (SVR)
- mixed venous blood gas measurement

Descriptive statistics (N, mean, SD, CV% mean, geometric mean, CV% geometric mean, median, min, and max) summarizing RHC parameters and their changes from baseline will be summarized by visit/time for treatment group assigned in the parent study and overall.

Panels of individual spaghetti plots over time/visit for treatment group assigned in the parent study and overall for each RHC parameter will be provided.

All RHC parameters will be listed by participant, and visit and if ranges are available, abnormalities will be flagged.

Echocardiography/RVF

The echocardiography is performed to assess the impact of study drug on right heart structure and function. All echocardiography images will be centrally read by an imaging vendor. The measurement is taken at baseline and at visit on Day 176 and 358.

The assessed echocardiography parameters include:

- Tricuspid annular plane systolic excursion (TAPSE)
- Tricuspid annular systolic velocity (TASV)
- Peak velocity of excursion (RV S')

- Fractional area change (FAC)

Descriptive statistics (N, mean, SD, CV% mean, geometric mean, CV% geometric mean, median, min, and max) summarizing echocardiography parameters and their changes from baseline will be summarized by visit/time for treatment group assigned in the parent study and overall.

Panels of individual spaghetti plots over time/visit for treatment group assigned in the parent study and overall for each echocardiography parameter will be provided.

All echocardiography parameters will be listed by participant, and visit and if ranges are available, abnormalities will be flagged.

Time to clinical worsening (TTCW)

TTCW will be defined as time to any of the following events

- Death
- Hospital stay (≥ 24 h) due to worsening of PAH. Worsening of PAH is defined by the following right heart failure related signs and symptoms: syncope or near syncope, cyanosis, increase of breathlessness, clinically relevant deterioration of exercise capacity, decrease of oxygen saturation, increased peripheral edema, hepatomegaly, and ascites
- Worsening of PAH resulting in need for lung transplantation or balloon atrial septostomy
- Initiation of parenteral prostanoid therapy, chronic oxygen therapy, or any other PAH-specific therapies or need for increase of diuretics for more than 4 weeks due to worsening of PAH
- Disease progression (switch in modified New York Heart Association/WHO FC by at least one grade)
- Significant drop in 6MWD (15% from baseline or more) due to PAH-worsening

Time to clinical worsening will be analyzed using survival models (i.e., Kaplan-Meier, cox regression) if adequate number of events occur during the study to characterize the survival curve. Participants without the event will be considered as censored at the end of the time at risk. The hazard ratio between the treatment group assigned in the parent study and the corresponding 80% confidence intervals will be computed using the appropriate method. If there is no adequate number of events, the number (and percentage) of participants with clinical worsening will be summarized by treatment group assigned in the parent study and overall.

NT-proBNP

Descriptive statistics (N, mean, SD, CV% mean, geometric mean, CV% geometric mean, median, min, and max) summarizing N-terminal fragment of the prohormone B-type natriuretic peptide , NT-proBNP (visits on Day 29, 85, 176, 267 and 358) and its changes from baseline will be summarized by visit/time for treatment group assigned in the parent study and overall.

Spaghetti plot over time/visit will be provided. And the endpoint will be listed by participant, and visit and if ranges are available, abnormalities will be flagged.

Change from baseline for efficacy endpoints will be descriptively summarized by visit/time for treatment group assigned in the parent study, and overall. The baseline measurement for the extension will be the baseline measurement taken during the parent study CLTP001A12201. Graphs (e.g., spaghetti plot) will be provided to show individual time courses of parameters for the extension study together with the parent study.

Additionally, changes from baseline for efficacy endpoints will be descriptively summarized by visit/time for treatment group assigned in the parent study, and overall using a different baseline strategy: participants receiving LTP001 in the parent study will use the baseline of parent study as the baseline; participants switching from placebo in parent study to LTP001 in extension study will use the baseline of extension study as the baseline.

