2.1 Data analysis general information

The final CSR analysis will be performed by Novartis Trial Statistician (TS) and Trial Programmer (TP). SAS version 9.4 or higher (SAS Institute, Cary NC) or later software will be used to perform all data analyses and to generate tables, figures, and listings.

Two change from baseline values will be reported for all the analyzed parameters planed in this document for this study:

- Change from baseline of the parent study (LTP001A12201, prior to the treatment start on Day 1)
- Change from baseline of the current extension study (LTP001A12201E1, parent study week 25)

The comparisons of these two change from baseline values and the treatment group difference within each change from baseline value will be reported.

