2.6.2 Statistical hypothesis, model, and method of analysis

Most analyses will be conducted descriptively using summary statistics and visualization of the time course for each endpoints using graphical presentations (e.g. spaghetti plots). statistical models may be used when data allows for TTCW. Detailed method of analyses are specified under each endpoint in [Section 2.6.1.1](#).

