5.4 Statistical models

Not applicable.

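### The parent-arm differences promised for the continuous efficacy endpoints have no confidence interval and no baseline adjustment, although both cost little

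*SAP*

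**What the plan says.** SAP 2.1 defines two changes from baseline, one from parent-study Day 1 and one from parent Week 25, and commits to a contrast on both: "The comparisons of these two change from baseline values and the treatment group difference within each change from baseline value will be reported". SAP 2.6.1.1 repeats this for efficacy as item b): "the treatment group difference (assigned in the parent study) within each change from baseline value".

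The statistics behind that contrast are given endpoint by endpoint. For 6MWD they are "Descriptive statistics (N, mean, SD, CV% mean, geometric mean, CV% geometric mean, median, min, and max) summarizing 6MWD parameters", and the same list is used for RHC, echocardiography and NT-proBNP. It contains no standard error and no interval.

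SAP 2.6.2 sets the general approach: "Most analyses will be conducted descriptively using summary statistics". The only exception it names is that "statistical models may be used when data allows for TTCW". SAP 5.4, on statistical models, is marked not applicable. For TTCW, if there are enough events, SAP 2.6.1.1 plans a hazard ratio between the parent arms with an 80% confidence interval.

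Protocol 9.4.1 plans descriptive summaries of these endpoints by parent arm and overall. The explicit between-arm difference appears only in the SAP.

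**The concern.** A difference between two small groups is hard to read without a statement of its uncertainty. The SAP supplies one when it compares these arms on TTCW, but not when it compares the same arms on the continuous endpoints.

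The numbers may be used. Protocol 1.1 gives the purpose as judging whether LTP001 merits further development. Protocol 4.1 says that efficacy seen here and in the parent study bears on whether the extension continues, and Protocol 7.6 lists inadequate efficacy and safety among the grounds for termination.

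Baseline is the second issue. With about 20 per arm, the parent baselines can differ noticeably by chance, and an unadjusted difference in change carries part of that imbalance. The parent Day 1 value is already defined (SAP 2.1.1) and already used to form the change, so adjusting for it needs no new data.

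**Working it through.** **No planned figure to reproduce.** Protocol 9.9 and SAP 3 mark sample size as not applicable. The documents give no SD, no parent allocation ratio, no baseline-to-follow-up correlation and no expected number with Week 26 or Week 52 data.

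**Inputs**
- N = 40: the approximate number expected to complete the parent study and meet the entry criteria (Protocol 5). The analysed number may be smaller.
- Allocation 1:1, with 2:1 and 3:1 as alternatives: assumed.
- Correlation ρ between parent baseline and follow-up, 0.3 to 0.95, with equal SD at both times: assumed.
- Interval level 80%: the level used for TTCW.

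**Step 1. Precision of the raw difference, in SDs of the change score.** Half-width = t(0.90, N−2) × √(1/n₁ + 1/n₀).
- 1:1 (20 and 20): 1.304 × √(2/20) = 1.304 × 0.316 = 0.41. The 95% half-width is 0.64.
- 2:1: 1.304 × 0.335 = 0.44.
- 3:1 (30 and 10): 1.304 × 0.365 = 0.48.
- If only 30 are analysed: 0.48 at 1:1, rising to 0.55 at 3:1.

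With no true difference, about one estimate in five would exceed its 80% half-width by chance.

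**Step 2. Effect of a chance baseline imbalance.** With 20 per arm, the standard error of a baseline difference is √(2/20) = 0.316 cross-sectional SD, so an imbalance of 0.3 SD is ordinary. If it arose by chance, it shifts the raw change difference by (1−ρ) × 0.3, in the opposite direction to the imbalance:
- ρ = 0.5: 0.5 × 0.3 = 0.15 SD
- ρ = 0.7: 0.3 × 0.3 = 0.09 SD

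These are cross-sectional SDs. The SD of change is √(2(1−ρ)) times as large: 1.00 at ρ = 0.5 and 0.77 at ρ = 0.7. The half-width of 0.41 from Step 1 is therefore 0.41 and 0.32 cross-sectional SD respectively.

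**Step 3. Gain from ANCOVA on the parent baseline.** The large-sample ratio of standard errors, ANCOVA to raw change, is √((1+ρ)/2): 0.866 at ρ = 0.5 (a 13% cut) and 0.922 at ρ = 0.7 (8%).

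Allowing for the lost degree of freedom at 20 per arm, the 80% half-widths in cross-sectional SD are:
- raw change: t(0.90, 38) × √(4/40) × √(2(1−ρ))
- ANCOVA: t(0.90, 37) × √(4/40) × √((1−ρ²) × 37/36)

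| ρ | Raw change | ANCOVA |
|---|---|---|
| 0.3 | 0.488 | 0.399 |
| 0.5 | 0.412 | 0.362 |
| 0.7 | 0.319 | 0.299 |
| 0.9 | 0.184 | 0.182 |
| 0.95 | 0.130 | 0.131 |

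The interval is about 18%, 12%, 6% and 1% narrower at ρ = 0.3, 0.5, 0.7 and 0.9, and no narrower at 0.95. A simulation of 8,000 runs with 20 per arm agrees: mean 95% half-widths are 0.635 against 0.558 at ρ = 0.5, and 0.491 against 0.459 at ρ = 0.7.

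**The case against.** The strongest defence is that this is an uncontrolled safety extension. Its primary objective is safety, estimands and sample size are marked not applicable, the protocol itself asks for descriptive efficacy summaries, and no test or decision rule rests on item b). Modelled differences could also invite more inference than the design supports. This limits the weight of the point and is why the added estimate should be labelled exploratory. It does not explain why a difference is promised without an interval when the same contrast for TTCW has one.

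The SAP does not forbid an interval or an adjustment. The gap is read from the listed statistics and from silence. SAP 5.4 proves little by itself, since the SAP plans Cox regression elsewhere, and SAP 2.6.5 assumes that missing 6MWT data are missing at random without naming a model. N, mean and SD are tabulated by parent arm, so a reader could work out an unadjusted interval by hand. All of this stands, and it means the uncertainty would be left for the reader to compute rather than hidden.

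Two stronger readings are tempting:
- **A reader might infer that the raw difference is in general more biased than the adjusted one.** That holds only for chance imbalance that regresses to a common mean. Those who enter are parent completers who wish to continue and whom the investigator expects to benefit (Protocol 4.1 and 5.1). If that selection left a stable 0.3 SD difference between arms, the change score would be unbiased and ANCOVA would be off by the same 0.15 to 0.09 SD. The documents do not show which case applies, and adjustment does not remove the selection.
- **A reader might infer that change from the extension baseline is a worse-affected version of the same comparison.** SAP 2.6.1.1 labels it the short-term effect. Arms that already differ at Week 25 because LTP001 worked are part of that question, in which one arm continues and the other starts. It needs an interval and careful labelling, but it is not an error.

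**Conclusion.** The point holds as a gap in specification. The SAP promises parent-arm differences for the continuous efficacy endpoints and specifies neither an interval nor a baseline adjustment.

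Under 1:1 allocation of 40 participants, a raw difference smaller than about 0.41 SD of change lies inside its own 80% interval half-width. An ordinary chance imbalance in the parent baseline could move it by 0.09 to 0.15 cross-sectional SD. The interval is the more important addition because it is useful whatever the correlation. The adjustment protects against chance imbalance and brings a modest precision gain, which vanishes for endpoints that track their baseline very closely.

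Allocation, correlation and analysed N are assumptions throughout. These are secondary, descriptive analyses, so the change is worth making before database lock but does not affect the primary objective.

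**What to change.** In SAP 2.6.1.1 item b), with matching wording in 2.1, 2.6.2 and 5.4:

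- Give every descriptive parent-arm difference in change an 80% confidence interval, including differences in change from the extension baseline.
- Beside it, report the parent-arm difference with an 80% interval from an ANCOVA of the value, with the parent-study Day 1 value as covariate. Do not substitute the Week 25 value as covariate: it is measured after randomised treatment and would not be equivalent.
- Do this at the visits where each endpoint is measured: RHC including PVR at Week 26 only, 6MWD and echocardiography at Weeks 26 and 52, and NT-proBNP at its scheduled visits.
- Use the log scale for PVR and NT-proBNP, in line with the geometric means already planned.
- Label the result exploratory, as earlier versus later start of LTP001, and state that adjustment does not remove selection into the extension.
- Keep the descriptive tables, plots and listings.

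The cost is a little programming and SAP wording, and one degree of freedom per model. No new data are needed.
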